**5.3.11. Determination of Nickel Sulfate Sensitivity**

During the Screening period, subjects will be tested to confirm the presence of cutaneous nickel sensitivity using the 1, 2.5, and 5% nickel sulfate patch. The test site will not be in the same area where patches will be placed at Baseline. The concentration of nickel sulfate for each subject that causes no greater than a ++ cutaneous reaction (2 out of 4, International Contact Dermatitis Research Group [ICDRG] scoring scale will be the concentration administered at Baseline (Day 1).

**5.3.12. Nickel Sulfate Patch**

At baseline the nickel sulfate patch will be applied. For Treatment regimen 1, the nickel sulfate patches will be applied and the subject will return within 48 hours for removal and to begin treatment intra-dermal injections. For Treatment regimen 2, the nickel sulfate patches will be applied at baseline after 10 minutes post-injection of either rHuPH20 or placebo.

The concentration of nickel sulfate (1, 2.5, or 5%) will be determined during the Screening period. Once the concentration is confirmed, this will be the concentration applied on the subject at the baseline visit.

At the baseline visit, the patches will be inoculated with the correct nickel sulfate concentration. The procedure for using the allergy patch system is found in [Appendix C](#).

### **5.3.13. Trans-Epidermal Water Loss (TEWL)**

All measurements should be conducted in an enclosed room in which air movement is minimized. Subjects must equilibrate for 30 minutes prior to testing in the controlled environment of 72 plus/minus 2 degrees F and a relative humidity (RH) of less than 50% prior to measurement reading. Make sure the skin area to be read is dry and clean. Press and securely hold the evaporimeter probe to the skin surface for 45 seconds. A validated Evaporimeter Operator should only be used to collect data.

### **5.3.14. Digital Photographs**

In these clinical photographs, for the duration of the study, the only variable allowed to change is the skin condition itself. Therefore, anything extraneous to the condition (jewelry, clothing, furniture, walls, etc.) is to be eliminated from the fields to be photographed, from the baseline through the final photographs. The necessity of good end-of-study photos should be stressed to the subjects to ensure their cooperation. Lighting, framing, exposure and reproduction ratios must be held constant. In the end, the pictures should read like a time-lapse movie. Detailed instructions are found in [Appendix D](#).

### **5.3.15. Chromometer**

Make sure the skin area to be read is dry and clean. To collect data, position the device directly over the skin area without applying pressure to the skin surface. Ensure the position of the device on the skin is level or parallel with the surface of the skin. Press the trigger once on the chromometer. A reading will be recorded on the program. Data collection should be done by a validated Chromometer Operator only.

### **5.3.16. Adverse Events**

Each study participant will be carefully monitored for the development of adverse events ([Section 7](#)).

### **5.3.17. Injection Site Assessment**

An assessment of local tolerability at the injection site will be performed prior to and 10 minutes after the injection for site reactions such as erythema, pruritus, and edema. If an injection site reaction is observed, it must be recorded as an adverse event. Local tolerability will be assessed by a qualified person.

### **5.3.18. Prior/Concomitant Medications**

Review any concomitant medications the subject is taking at each study visit, beginning 21 days prior to Visit 1. See [Section 4.3](#) for a list of prohibited medications.

#### **5.4. Premature Termination of Treatment/Withdrawal of Subjects**

The Investigator must guard the subject's welfare and should discontinue study drug treatment at any time that this action appears to be in the subject's best interest. Subjects may discontinue study drug treatment and may withdraw or be removed from the study at any time. Possible reasons for such actions may include, but are not limited to, the following:

- The occurrence of serious or unexpected unwanted effects attributable to the study drug(s) or study procedure(s)
- In the event of abnormal laboratory results judged to be related to study drug(s) or study procedure(s) and of clinical significance
- Any significant protocol violation (including demonstrated lack of compliance)
- Serious difficulty in obtaining blood samples
- Enrolled subject withdraws consent
- Intercurrent illness requiring medication that might interfere with the study
- Other reasons as determined by the Investigator

It is the right and duty of the Investigator to interrupt the treatment of any study subject whose health or well-being may be threatened by continuation in this study.

Once a study subject has received study drug under this protocol, the subject must be followed for safety as required in the protocol (see [Section 7](#)). In the event that a study subject discontinues treatment prematurely, every effort will be made to document the reason for premature termination and obtain follow-up safety data.

Should the enrollment rate lag or significant numbers of clearly non-eligible and/or non-evaluable subjects be entered in the study, Halozyme may elect to terminate the study at any and all investigational sites. Halozyme also has the right to terminate the study at any time for non-adherence to protocol, unavailability of the Investigator or his or her study staff for Halozyme or its designated monitoring personnel, or for administrative reasons, at any time.

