## **5.2. Subject Replacement/Completion Criteria**

Subjects who are not evaluable will be replaced. An evaluable subject is one who has completed dosing (or prematurely discontinued the administration due to a toxicity) and has undergone sufficient assessments to allow an assessment of the tolerability of the administration.

As this study is being conducted at a single site, the site personnel, in conjunction with the Sponsor, will make the determination when a subject will need to be replaced in the study. This information will be collected on the Enrollment Log. Each subject not meeting the completion criteria will be replaced by the enrollment of an additional subject. In the event that a subject withdraws from the study prematurely or does not meet the completion criteria, every effort will be made to document the reason for termination and obtain follow-up safety data.

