cutaneous reaction an ID syringe push bolus injection of either rHuPH20 or placebo control. Each injection will be administered once daily for 5 days. Prior to each daily injection, subjects will be evaluated for efficacy, safety, and tolerability. A final evaluation will be conducted 7 days after the last dose of study treatment.

Treatment Regimen 2 (TR2-5 – TR2-8):

This regimen will assess the prevention and treatment of contact allergy to nickel sulfate. Each subject will receive in the center of each lower space on the back, either an ID syringe push bolus injection of rHuPH20 or placebo control. Exactly 10 minutes after the injection, a single row of four patches (1, 2.5, or 5% nickel sulfate patches; determined for each subject during the Screening period) will be placed over the center of the ID injection. After 48 hours, the patches will be removed and an assessment will be made of the reaction site as per the ICDRG scoring system. The subject will receive an ID injection of the same study drug from pre-treatment in the center of the cutaneous reaction once daily for 5 days. Subjects will be evaluated for efficacy, safety, and tolerability, on a daily basis. A final evaluation will be conducted 7 days after the last dose of study treatment.

For a given subject, the anticipated duration of time on study is up to 35 days, which include Visit 1 (screening, within 21 days prior to receiving study drug), Visit 2 (Day 1), Visit 3 (Day 3), Visits 4 – 7 (Day 4 – 7) and Visit 8 (Day 14).

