5. ANALYSIS POPULATIONS

The ITT population will include all enrolled subjects (all subjects who got a subject identification number assigned at the time of study enrollment in anticipation of receiving a dose of study drug).

The Safety population will include all subjects who receive at least one dose of study drug.

The Evaluable population will include all evaluable subjects. An evaluable subject is one who has completed dosing (or prematurely discontinued the administration due to a toxicity) and has undergone sufficient assessments to allow an assessment of the tolerability of the administration.

A subject is considered to have undergone sufficient assessments to allow an assessment of the tolerability of the administration if the subject has at least one ICDRG score reported on Day 4 or later.

A subject is considered to have prematurely discontinued the administration due to toxicity if the subject has Adverse Event checked as the reason for not completing the study on the Study Completion/Termination CRF page, and has Drug Withdrawn as the action taken with study drug checked on the Adverse Event CRF page.

Efficacy analyses will be run on the Evaluable population and the ITT (Intent-to-Treat) population. Analyses run on the Evaluable population will be considered the primary analyses.

Safety analyses will be run on the Safety population.

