8.1 Primary Variables

The primary efficacy endpoint will be based on the International Contact Dermatitis Research Group (ICDRG) Scoring Scale. Using the ICDRG Scoring Scale, each score will be assigned a Sponsor-defined “grade”. Scores with stronger reactions will be assigned grades with higher values with a maximum grade of 3; scores with weaker reactions will receive lower values with a minimum grade of 0. Grade assignments based on the ICDRG Scoring Scale are shown in the table below.

International Contact Dermatitis Research Group (ICDRG) Scoring Scale

Grade	Score	Interpretation
0	-	Negative reaction
1/2	?	Doubtful reaction; faint macular erythema only
1	+	Weak (nonvesicular) positive reaction; erythema, infiltration, papules, vesicles
2	++	Strong (vesicular) positive reaction; erythema, infiltration, papules, vesicles
3	+++	Extreme positive reaction; bullous reaction
NA	IR	Irritant reaction of different types

Treatment effect of rHuPH20 or placebo control injection on the exposure to topical nickel allergen will be assessed using ICDRG grades for Treatment Regimens 1 and 2 at Day 3 through Day 7 and Day 14.

Regimen 2 only: For each subject, the day of maximal ICDRG score will be determined for each injection type (rHuPH20 and Placebo). The maximal ICDRG score will be the highest score reported for each subject. If the maximal ICDRG score for a particular subject is reported more than one time, the first instance will be used to determine the day when the maximal ICDRG score was reached.

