8.5 Handling Missing Data

No missing values will be imputed.

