9.1 Statistical Analyses

The primary analysis is the pair-wise intra-subject comparison of endpoint parameters for the injections with and without rHuPH20. The secondary analysis covers safety and other endpoint parameters (see Section 10).

ICDRG scores will be shown for Treatment Regimen 1 and Treatment Regimen 2 by injection types (rHuPH20 or Placebo) at Baseline, Day 4, Day 5, Day 6, Day 7 and Day 14. ICDRG scores will be reported by subject using figures (Figure 1) and listings (Listing 8).

A qualitative medical review of the ICDRG scores will be used to investigate:

- Possible treatment effect of rHuPH20 or placebo control injection on the exposure to topical nickel allergen.
- Proportion of subjects that have a ≥ 1 grade reduction in at least one patch region.

At the conclusion of the study, findings from the medical review will be summarized in the clinical study report.

For Treatment Regimen 2, the day of maximal ICDRG Score will be used to assess the possible effect each injection type has on the onset of reaction to topical nickel allergen. The day of maximal ICDRG Score will be summarized for each injection type using counts and percentages (Table 6.1/6.2). Possible days of maximal ICDRG Score include

the following: Day 4, Day 5, Day 6, Day 7, and Day 14. If the maximal ICDRG Score for an injection type occurred prior to treatment, the subject will be reported as never having had an ICDRG Score more severe than Day 3 for summary purposes.

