TEWL (Trans-Epidermal Water Loss) Assessment (g/m²h)

Subject	Visit	Was TEWL Completed?	Collection Date/Time	Result							
				TR 1-1	TR 1-2	TR 1-3	TR 1-4	TR 2-5	TR 2-6	TR 2-7	TR 2-8
	Day 1										
	Day 3										
	..										

path\t_program.sas date time

Listing 45
Digital Photographs

Subject	Visit	Were Digital Photos Taken?	Collection Date	Collection Time	Uploaded to Website?
		No:reason			No:reason

path\t_program.sas date time

Listing 46
Chromometer
Part 1 of 3: a-Scale

Subject	Visit	Was a Chromometer Reading Completed?	Collection Date	Collection Time	Category	TR 1-1	TR 1-2	TR 1-3	TR 1-4	TR 2-5	TR 2-6	TR 2-7	TR 2-8
	Day 1	No:reason											
	Day 3				Result Change from Day 1								

path\t_program.sas date time

Listing 11
Chromometer
Part 2 of 3: b-Scale

Subject	Visit	Was a Chromometer Reading Completed?	Collection Date	Collection Time	Category	TR 1-1	TR 1-2	TR 1-3	TR 1-4	TR 2-5	TR 2-6	TR 2-7	TR 2-8
	Day 1	No:reason											
	Day 3				Result Change from Day 1								

path\t_program.sas date time

Listing 11
Chromometer
Part 3 of 3: l-Scale

Subject	Visit	Was a Chromometer Reading Completed?	Collection Date	Collection Time	Category	TR 1-1	TR 1-2	TR 1-3	TR 1-4	TR 2-5	TR 2-6	TR 2-7	TR 2-8
	Day 1	No:reason											
	Day 3				Result Change from Day 1								

path\t_program.sas date time

Listing 47
Subject Diary

Subject	Visit	Mark if Not Done	Not Done Reason	Date	Start Time	End Time	Symptom	Severity[1]	Comments	Dispense next Diary to subject?
						ongoing				

[1] 1 – Least Discomfort, 5 – Most Discomfort.

path\t_program.sas date time

Listing 48
Screening Nickel Sulfate and Vehicle Control Patches

Subject	Application of Patches				Test Results (48 Hours After Application)						
	Patches Applied?	Date	Time	Date	Time	48 hours After App.?	ICDRG			Dose Assigned?	Assigned Dose
No:reason				No:reason				No:reason			No:reason
path\t_program.sas	date	time					1%	2.5%	5%		

Listing 49
Study Drug Administration – Treatment Regimen 1
Part 1 of 4: Application of Nickel Sulfate Patches

Subject	Visit	Treatment Date	8 Areas Normal?	Application Time	4 Patches applied?	Concentrations of Nickel Sulfate
No:reason						

path\t_program.sas date time

Listing 14 (cont.)
Study Drug Administration – Treatment Regimen 1
Part 2 of 4: Physical Examination Prior to Injection

Subject	Visit	Subject Randomized?	Treatment Date	Asse. Time	ICDRG Score				AE #			

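### The plan does not say whether reaction scoring continues after injections stop, and the Regimen 2 day-of-maximum table then reads cut-off scores as complete follow-up

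*Protocol*

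**What the plan says.** **Data pursued after stopping.** Protocol section 5.4 treats stopping study drug and leaving the study as separate events. For a subject who stops treatment, "every effort will be made to document the reason for premature termination and obtain follow-up safety data". Section 5.2, on withdrawal or failure to meet the completion criteria, is parallel: "every effort will be made to document the reason for termination and obtain follow-up safety data". Neither mentions ICDRG scoring.

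**When scores are taken.** Appendix A of the protocol schedules a test area assessment at each visit on Days 3 to 7 and on Day 14. For Regimen 1, SAP section 3 says "Prior to each daily injection, subjects will be evaluated for efficacy, safety, and tolerability"; for Regimen 2 it says evaluation is daily. In SAP Appendix C the ICDRG scores sit on the drug-administration listings, for Regimen 1 under "Part 2 of 4: Physical Examination Prior to Injection", with a matching part for Regimen 2.

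**Who is analysed.** SAP section 5: "An evaluable subject is one who has completed dosing (or prematurely discontinued the administration due to a toxicity". The assessment requirement is met by one ICDRG score on Day 4 or later. A toxicity stopper is identified by two entries: an adverse event as the reason for not completing the study, and drug withdrawn as the action taken. Evaluable-set analyses are primary.

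**How the scores are used.** For Regimen 2, SAP section 8.1 says "The maximal ICDRG score will be the highest score reported for each subject", and the first occurrence fixes the day. Section 8.5: "No missing values will be imputed". Under section 9.1, if the maximum came before treatment, "the subject will be reported as never having had an ICDRG Score more severe than Day 3 for summary purposes". Table 6.1 (Evaluable) and Table 6.2 (ITT) have six rows: that *Never* row and Days 4, 5, 6, 7 and 14.

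**The concern.** The *Never* row states that a reaction was watched and did not get worse. The rule that fills it needs only that no reported score exceeded Day 3. For a subject whose scores end early, these are different statements, and the table cannot tell them apart.

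Two features of the plan make this a practical matter. Someone who stops for toxicity is deliberately kept in the primary set on a single later score. The SAP also recognises such a subject by her not completing the study, so missing late scores are likely for exactly this group. At stake is the description of time to onset in Regimen 2, which is part of a primary objective. Table 6 is the only efficacy table in the SAP's list of tables.

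**Working it through.** **Starting point.** There is no figure to reproduce. Twenty evaluable subjects and a maximum of 30 enrolled are stated without alpha, power, effect size or stop rate, and no formal comparison is planned. The check is therefore of the classification rule.

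**Readings at risk.** Scoring days after Day 3 are 4, 5, 6, 7 and 14, which is 5. If the last score is on Day 4, up to 4 are missing (5, 6, 7, 14). Regimen 2 has 4 sites, so 4 × 4 = 16 of 5 × 4 = 20 site scores are missing. With no later score, only *Never* and Day 4 are reachable, and 6 − 2 = 4 of the 6 rows are closed to her.

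**Applying the rule** (first day of the highest reported score; Day 3 becomes *Never*) to illustrative sequences for one injection type on Days 3, 4, 5, 6, 7, 14:

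| Sequence | Full follow-up | Last score Day 4 | Last score Day 5 |
|---|---|---|---|
| ++, ++, ++, +++, +++, + | Day 6 | Never | Never |
| ++, ++, +++, +++, ++, − | Day 5 | Never | Day 5 |
| +, +, +, +, +, ++ | Day 14 | Never | Never |
| +, ++, ++, +++, +++, + | Day 6 | Day 4 | Day 4 |

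The first three show truncation reported as no worsening. The fourth shows the other outcome: the subject had already exceeded Day 3, so she is misdated and does not enter *Never*.

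**How often each error arises over possible patterns.** Take every sequence with a Day 3 grade of 1 or 2, each later grade drawn from 0, 1/2, 1, 2, 3, and a true maximum after the last score. The share labelled *Never* is:

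- last score Day 4: 3108/(3108 + 369) = 89.4%
- last score Day 5: 1858/(1858 + 427) = 81.3%
- last score Day 6: 1008/(1008 + 333) = 75.2%
- last score Day 7: 418/(418 + 175) = 70.5%

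The remainder get a day that is too early. These are unweighted counts of patterns, not probabilities of what would be seen in patients.

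**Size in the table.** Each subject contributes one result per injection type, so one misplaced subject moves a cell by 100/20 = 5 percentage points (100/30 = 3.3 if 30 are in the ITT table).

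**Chance that it arises.** The stop rate p is an assumption. P(at least one stopper among 20) = 1 − (1 − p)^20:

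| Assumed p | Expected stoppers (20p) | P(at least one) |
|---|---|---|
| 2% | 0.4 | 0.33 |
| 5% | 1 | 0.64 |
| 10% | 2 | 0.88 |
| 20% | 4 | 0.99 |

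**The case against.** The strongest reply is that scoring does not depend on an injection. Appendix A schedules it by visit, including Day 14, when no dose is given. The administration listings have a field for an injection not given, with a reason. The wording that ties efficacy evaluation to each injection belongs to Regimen 1, whereas Table 6 covers Regimen 2. A Day 14 score, if taken, would be used. This stands. A reader might infer that the plan ends scoring when injections end, but the documents do not say so. What is missing is a statement that the schedule applies to someone who has stopped. The final evaluation is also described as 7 days after the last dose. Read literally, that is Day 11 for a last dose on Day 4 (4 + 7), and Table 6 has no such row.

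Second, local worsening would not vanish. Injection-site reactions are recorded as adverse events, and those judged related are followed until resolved or stabilised. Figure 1 prints NR for unreported scores, and Listing 1 shows the last injection date and the reason for not completing. With about 20 subjects a careful reader could find the gaps. This also stands, but an adverse event record is not an ICDRG grade, and Table 6 itself would still show *Never*.

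Third, every subject carries both rHuPH20 and placebo sites, so stopping the subject truncates both columns together. This is correct and limits the consequence. A reader might infer a biased treatment contrast, but that requires late worsening to differ by injection type, and nothing in the documents shows that it does.

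Fourth, two further inferences lack support. Toxicity stoppers need not be those with the worst local course, since a stop may follow a systemic event. Nor does the ITT run become pointless, because it also includes non-evaluable and replaced subjects.

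**Conclusion.** The point holds as a gap between the two documents and a labelling fault in Table 6. If scores are not taken after stopping, the stated rule places a subject who worsens later in *Never* when no earlier score exceeded Day 3, and otherwise assigns a day that is too early. A subject last scored on Day 4 lacks up to 16 of 20 Regimen 2 site scores. Counting 32 of 40 would bring in Regimen 1, to which the rule does not apply.

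Each such subject can shift a cell by 5 percentage points at 20 subjects. The description in each column is affected; the contrast is affected only under the added assumption that late worsening differs by type. The total effect depends on a stop rate that the documents do not give and that could be zero. It is worth correcting because the table reports onset, part of a primary objective, and the correction is small.

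**What to change.** 1. In Protocol sections 5.2 and 5.4, state that a subject who stops injections but has not withdrawn consent continues ICDRG scoring at the remaining scheduled visits through Day 14, alongside the safety follow-up already required.
2. In SAP section 9.1 and Tables 6.1/6.2, add a row *follow-up incomplete, last score Day x* for subjects whose scores do not run through Day 14, and keep them out of *Never*. The cut-off must be Day 14, because Day 14 is itself a row. A footnote can count subjects who have a Day 14 score but a gap before it.
3. In SAP section 5, identify a toxicity stopper by drug withdrawn for an adverse event and drop the condition of not completing the study. Otherwise a subject who stops drug but stays for scoring could be marked as completing the study and fall out of the Evaluable set, so that the first change would undo the inclusion the SAP intends.

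The cost is a short protocol clarification, one table row and one definition. The scoring is a visual grade at visits already scheduled. The downside is that some stopped subjects attend a few more visits.
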